## Appendix 2: Standard operating procedure to apply Mepilex® Border Heel on intact skin

Deutsch	English

Inhaltsverzeichnis
 
 
1. Beschreibung des Produkts
 
2. Vorbereitungen
 
3. Arbeitsschritte
 
4. Besondere Anweisungen
 
5. Mögliche Fehler/Störungen/Problem-Lösungen
 
6. Lagerbedingungen / Reinigung
 
	
Table of Contents
 
 
1. Description of Device
 
2. Preparation
 
3. Workflow
 
4. Special Instructions
 
5. Possible Error/Disruptions/Problem Solutions
 
6. Storage Conditions/Cleaning
 

1. Beschreibung des Produkts
 
Mepilex® Border Heel ist ein speziell an die Fersenform angepasster Schaumverband. Er ist weich, gut anpassungsfähig und wasserfest. Der Verbandswechsel erfolgt nahezu schmerzfrei und atraumatisch. Der Schaumverband ist selbsthaftend. Eine sekundäre Fixierung ist nicht erforderlich, sodass keine Rückstände auf der Haut verbleiben.
 
Der Verband wird alle 3 Tage gewechselt.
 
Lieferumfang zum Produkt: /        Mölnlycke Health Care        Mepilex® Border Heel
 
 
• 18,5cm x 24cm
 
	
1. Description of Device
 
Mepilex® Border Heel it is a special foam dressing for prevention of heel area pressure ulcer. It is very smooth and flexible/adaptable and water-resistant. Changing is nearly painless and non-traumatic.
 
Remove and replace dressing after 3 days.
 
Delivery contents of the device:
 

2. Vorbereitungen
 
Bestimmte Standards sollen vor und während der Applikation eingehalten werden.
 
 
a) Vorbereitung des Arbeitsplatzes:           
 
• Legen Sie sich zwei Schaumverbände bereit,
 
• Ziehen Sie sich Handschuhe an,
 
• Legen Sie sich bei Bedarf Waschlappen und Handtuch für die optimale Reinigung des Wundauflagegebietes bereit.
 
 
 
b) Lagern Sie den Patienten/Probanden bequem auf eine Seite, holen Sie bei Bedarf eine zweite Pflegekraft oder Lagerungsmittel zur Unterstützung.
 
	
2. Preparation of measurement
 
A set of standards should be maintained before and during the application.
 
 
a) Prepare a place/table with all material:           
 
• Prepare two dressings,
 
• Put on gloves,
 
• For cleaning the wound area provide washcloth and towel (only if necessary).
 
 
 
b) Place the patient on one site (support with pillows) maybe you need help of another colleague.
 
c) Prepare a dustbin.
 

c) Stellen Sie sich einen Abwurfbehälter bereit.
	

3. Arbeitsschritte
 
a) Inspektion der Ferse, entfernen Sie die Mitteltrennfolie. Säubern Sie bei Bedarf das Wundauflagegebiet, achten Sie darauf, dass die Haut trocken ist.
 	
3. Workflow
 
a) Remove the central release film. Assess application area (heel area).
 

b) Legen Sie den Schaumverband auf das Fersengebiet und entfernen Sie die Schutzfolie (markiert mit „B“).
  	
b) Apply the adherent part of the dressing marked “B” in the instructions for use illustration under the foot. Do not stretch.
 

c) Entfernen Sie nacheinander die Folie von den Seitenflügeln des Verbandes und fixieren ihn faltenfrei. Verband nicht auseinander ziehen!
  	
c) Remove the side flap protection film. Apply and smooth side-flap. Repeat with the other side. Do not stretch.
  

d) Ziehen Sie die restliche Schutzfolie auf beiden Seiten des Verbandes ab (markiert mit „A“) und fixieren ihn, wie auf der Abbildung dargestellt, unterhalb der Achillessehne. Verband nicht auseinander ziehen!
  	
d) Apply the adherent part of the dressing marked A on the instructions for use illustration on the Achilles' tendon. Remove the upper protection films on each side, apply, and smooth the dressing. Do not stretch.
 

e) Lagern Sie den Patienten in seitlicher Position oder auf den Rücken.
	
e) Remove the patient in a site or back position.

4. Besondere Hinweise
 
 
a) Tägliche Überprüfung des Verbandes und Dokumentationsführung.
 
b) Achten Sie darauf, dass die Verbandränder bei Entfernung oder Erneuerung des Schaumverbandes faltenfrei, glatt und fest kleben.
 
c) Der Verbandwechsel erfolgt alle 3 Tage anhand des Wund-Assessments und so lang der Patient einem Risiko ausgesetzt ist.
 
	
4. Special Instructions
 
 
a) Daily assessment of the dressing and documentation.
 
b) Removal and reapplication of dressing. Ensure the border of the dressing is smooth/even with no wrinkles.
 
c) Remove and replace dressing after 3 days as long as the patient is still at risk, replace dressing according to schedule on the Wound Assessment Form documentation.
 

5. Mögliche Störungen / Problemlösungen
 
 
a) Die Auflagefläche muss trocken und frei von Pflegeprodukten und eventuellen Pflasterresten sein, damit der Schaumverband gut auf der Haut haftet.
 
b) Keine zusätzlichen Pflegeprodukte verwenden.
 
	
5. Possible Error Messages/ Disruptions/ Problem Solutions
 
 
a) The application area must be dry and free of dimethicone, skin sealants, emollients and remove the center release film for good adhesion.
 
b) Don't use any other additional products.
 


6. Lagerung und Reinigung
 
 
a) Gestalten Sie Ihren Arbeitsplatz übersichtlich und sauber.
 
b) Lagern Sie die Wundverbände (Mepiplex® Border Heel) trocken und bei Raumtemperatur.
 
	
6. Storage Conditions/Cleaning
 
 
a) Clean and tidy up your workplace
 
b) Store the dressings Mepiplex® Border Heel at room temperature in a dry place.
 

## Appendix 3: Patient card

**Dieser Patient/ diese Patientin nimmt an der Studie zur Dekubitus-Prävention teil!**

1. Bitte achten Sie darauf, dass die Silikonverbände an Fersen und dem Sakralbereich glatt und fest kleben.

2. Inspizieren Sie die Verbände bei jedem Lagerungswechsel. Achten Sie bitte darauf, dass die Verbandränder faltenfrei kleben.

3. Falls sich der Verband gelöst hat, bringen Sie bitte einen Neuen an und kontaktieren Sie uns!

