### 3.3 Interventions

Within the study PU prevention for all patients follows the Charité university hospital pressure ulcer prevention standard (Charité-Universitätsmedizin Berlin 2012) (Figure 1).

Figure 1. Current pressure ulcer prevention standard at the Charité

This includes PU risk scoring and skin inspection within 6 hours after admission and depending on the risk categories “high risk” and “very high risk” the implementation of preventive measures including: (1) patient information, (2) daily skin inspection, (3) mobilization, (4) use of special support surfaces, (5) repositioning and (6) floating heels. Regarding general skin and incontinence care there are no other standards implemented at the moment.

In case of potentially meeting the inclusion criteria for the study a researcher/research assistant of the CRC team will check the in- and exclusion criteria using a screening form. If eligible the assignment to one of the study groups will be performed by this researcher. This will be also done within 6 hours after admission **to the ICU**.

If a patient is assigned to the intervention group the dressings Mepilex® Border Sacrum and Mepilex® Border Heel will be applied by the researcher/research assistant onto the respective intact skin areas according to the instructions of the manufacturer and according to the study SOP (see Appendices 1 and 2). Special care will be taken that the Mepilex® Border Sacrum is carefully applied and that no other skin care products are used between the skin and the dressings. The dressings will be renewed every 3 days by the researcher/research assistant. In case of becoming soiled or dislodged they are changed immediately by the nurses and/or by the researchers. Nurses on the participating ICUs and on general wards will be instructed accordingly. In addition, in the intervention group laminated patient cards will be posted at and/or near the bed serving as reminder and containing minimum information about how to apply the dressings and the contact of the responsible researcher (Appendix 3). Dressings remain onto the skin during the whole study period also including transfer to another ward. All other PU preventive care and treatment procedures are performed as usual according to the Charité PU prevention standard (Figure 1).

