## Secondary outcomes

Name	Method and metric	Time points of data collection
Pressure ulcer category II, III, IV, Unstageable, DTI at heels or sacrum	
 
• Clinical assessment using the NPUAP PU classification system
 
• Proportions developed per 1000 bed days (incidence)
 
	D0 and once daily
Pressure ulcer category I (non-blanchable erythema) at heels and/or sacral area	
 
• Clinical assessment using the NPUAP PU classification system
 
• Proportions developed from baseline until end of study (cumulative incidence)
 
	D0 and once daily
Pressure ulcer category I (non-blanchable erythema) at heels and/or sacral area	
 
• Clinical assessment using the NPUAP PU classification system
 
• Proportions developed per 1000 bed days (incidence)
 
	D0 and once daily
Days free of sacral and/or heels pressure ulcers category I, II, III, IV, DTI	
 
• Clinical assessment using the NPUAP PU classification system
 
• Number
 
	D0 and once daily
Resources associated with heel and sacral PU prevention	
 
• Preventive dressings (n), time for dressing application (minutes; data source: estimation)
 
• Type of support surface (standard, special elastic foam, viscoelastic foam, low air loss overlay/mattress, alternating air mattress; data source: clinical records and direct observation)
 
• Type of turning (30° degrees left/right, supine, prone, other; data source: clinical records)
 
	D0 and once daily
Resources associated with heel and sacral PU treatment	
 
• Wound assessments (number and times; data source: clinical records and estimation)
 
• Wound infection diagnoses, e.g. swabs, biopsies (number, times; data source: clinical records and estimation)
 
• Therapeutic primary and secondary dressings (numbers, types), time for dressing application/changes (minutes; data source: clinical records and estimation)
 
• Debridement (numbers and types incl. material; data source: clinical records and estimation)
 
• Systemic antimicrobial treatment because of PU wound (number, types; data source: clinical records)
 
	D0 and once daily

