**Figure 3. Data collection and management**

## 5.2 Statistical methods

Depending on the level of measurement (nominal, ordinal, continuous) variables will be described using absolute and relative frequencies or arithmetic means, medians and spread parameters (minimum, maximum, interquartile ranges, standard deviations). Baseline demographic (age, gender, PU risk etc.) and clinical characteristics (e.g. medical diagnoses, duration of ventilation) of each group will be displayed in a table.

The primary end point PU incidence category II, III, IV, DTI at heels and/or sacrum will be compared using a Chi-squared test. This will be the main analysis of this primary outcome. A logistic regression will be applied to adjust for baseline covariates. An alpha level of 5% (two-sided) will be applied. Kaplan-Meier analyses and logrank test will be used to compare the times to development of a new PU between groups. Multiple Cox regression analysis will be performed to adjust for potential confounders. Data will be analysed as intention to treat.

Secondary outcomes will be analysed in a similar way. Depending on the level of measurement (nominal, ordinal, continuous) secondary outcomes will be described using absolute and relative frequencies or arithmetic means, medians and spread parameters (minimum, maximum, interquartile ranges, SDs). Chi-squared or t-tests will be applied to compare groups. In case of normality assumption being violated, the Mann-Whitney U test will be used instead of t-test.

For daily measurements, missing values will be imputed via LOCF method, and the results will be compared to those without imputation.

A cost effectiveness analysis (CEA) comparing both groups will be conducted. Quantities of used preventive dressings including labor costs for application in the intervention group and quantities of used PU treatment materials (e.g. dressings, time) will be documented. Current market prizes in Euro will be used to calculate the total costs per group. An incremental cost effectiveness ratio (ICER) will be calculated by dividing the mean differences in costs by the mean differences in effects. In order to make results comparable a similar approach like the work by Santamaria et al. 2013b will be used.

All analytic steps including the CEA will be repeated for the two subgroups heel PUs and sacral PUs.

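### The cost-effectiveness analysis leaves out the dressing checks that the bedside card asks of ward nurses in the dressing arm only, so that arm's cost may be understated by an unknown amount

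*Combined protocol and SAP*

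**What the plan says.** **The task.** Item 2 of the patient card in Appendix 3 reads "Inspizieren Sie die Verbände bei jedem Lagerungswechsel", that is, look at the dressings each time the patient is repositioned; it also asks nurses to see that the edges lie without wrinkles. Section 3.3 limits the card to one arm: "in the intervention group laminated patient cards will be posted at and/or near the bed serving as reminder". The Special Instructions in both application SOPs (Appendices 1 and 2) add "Daily assessment of the dressing and documentation".

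**The cost rule.** For prevention, the cost-effectiveness paragraph of section 5.2 names "Quantities of used preventive dressings including labor costs for application in the intervention group". The matching resource outcome in section 3.4 is "Preventive dressings (n), time for dressing application (minutes; data source: estimation"). That outcome also records support surface and type of turning, but no time for checking. Assessment time is collected only under treatment of an ulcer that has already developed: "Wound assessments (number and times; data source: clinical records and estimation"). The ICER is formed "by dividing the mean differences in costs by the mean differences in effects".

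**Care in both arms.** The hospital prevention standard applies to every patient, and section 3.3 lists among its measures "2) daily skin inspection, (3) mobilization, (4) use of special support surfaces, (5) repositioning and (6) floating heels".

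**The concern.** Whether the dressings are cost effective is a stated secondary objective (section 2.2). A within-trial analysis should charge the intervention with the work that helped to produce its effect. Here the dressing arm is delivered with a recurrent check by ward staff, but the plan neither collects the time for that check nor says that it is deliberately excluded.

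An omitted cost that falls on one arm does not cancel in the difference. If the checks take any extra time, the dressing arm looks cheaper than it was, and never dearer. Section 5.2 repeats the analysis for heel and sacral ulcers separately, so the gap carries into those results. A reader of the final report could not tell whether the omission was negligible.

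**Working it through.** **1. Does the plan give a cost figure to reproduce?** No. It states no check time, turning frequency, length of participation, wage, price or ICER. The one related figure is the planned effect in section 3.6 (0.06 against 0.01), which would be the ICER denominator. The sample size built on it reproduces. With the pooled-variance formula and mean rate 0.035:

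n = [1.96 × √(2 × 0.035 × 0.965) + 0.842 × √(0.06 × 0.94 + 0.01 × 0.99)]² / 0.05² = 210.9, so 211 per arm as stated. The total is 422 × 1.10 = 464.

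The planned effect difference is therefore 0.06 − 0.01 = 0.05.

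**2. Which items are counted?**

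- Scheduled renewal every 3 days, changes of soiled or dislodged dressings, and replacement of a loosened dressing (card item 3) are all applications, so they are counted.
- Ward-nurse checks at each turn are not counted.
- Once-daily researcher checks of dressing fit are not counted. Section 3.3 lists them among the measures to improve adherence, within a daily visit that patients in both arms receive, so leaving them out is defensible.

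**3. How does an omitted cost pass through?** Let c be the uncounted check cost per dressing-arm patient, ΔC the cost difference and ΔE the effect difference (ulcers averted per patient).

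- Correct ICER = (ΔC + c)/ΔE, so the shift is c/ΔE. At ΔE = 0.05, each EUR 1 gives 1/0.05 = EUR 20 per ulcer averted.
- If ΔE is negative the ratio moves the other way. If ΔE is near zero the ratio is unstable.
- Incremental net benefit, λΔE − ΔC with λ the value of an ulcer averted, falls by c whatever the sign of ΔE. On that scale the omission can only favour the dressing.

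**4. Illustration.** c = minutes per check × turns per day × days × hourly wage/60. Every input here is an assumption.

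| Case | Min per check | Turns/day | Days | EUR/h | c (EUR) | Shift at ΔE = 0.05 | Shift at ΔE = 0.02 |
|---|---|---|---|---|---|---|---|
| No extra time | 0 | 6 | 10 | 35 | 0 | 0 | 0 |
| Low | 0.25 | 3 | 5 | 25 | 1.56 | 31 | 78 |
| Middle | 0.5 | 6 | 10 | 35 | 17.50 | 350 | 875 |
| High | 2 | 12 | 15 | 45 | 270 | 5,400 | 13,500 |

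Middle case: 0.5 × 6 × 10 = 30 minutes; 30/60 × 35 = EUR 17.50; 17.50/0.05 = EUR 350 per ulcer averted. The ΔE of 0.02 is an assumed smaller effect.

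**5. Can turns be counted from the planned data?** Only approximately. The other variables in section 3.4 include type of position and mean length of position in hours, recorded daily, but not the number of changes. Turns per day can be approximated as 24 divided by mean length in hours; for example, 24/4 = 6.

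**The case against.** The strongest reply is that the check may cost almost nothing. It is made during a turn, turning is standard care in both arms, and glancing at a dressing edge while the patient is already on one side may add no measurable time. This stands, and it is why the range must include zero.

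A second reply is that the card is a study instrument. It announces trial participation, asks staff to call the study team, and appears in section 3.3 among the adherence measures. Whether its checks belong in the cost of routine use is a question of costing perspective. Section 5.2 also says the approach will resemble a cited within-trial analysis, whose handling of checking time is not visible here. This stands as a reason to keep the planned analysis as the base case, but not for leaving the choice unstated.

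A reader might go further and infer that the checks are all extra work, because the hospital standard asks for skin inspection only once a day. The documents do not support this. Section 3.3 says what the standard includes, the figure is not in the text, and the full standard is a separate document. Nurses may already look at these sites at each turn in both arms.

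**Conclusion.** The gap is real and of minor weight. The dressing arm carries a card-mandated task whose time is neither collected, costed nor declared out of scope. Any resulting error in cost can only favour the dressing.

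A reader might infer that the dressing arm's cost and the ICER are definitely understated. The documents support only that cost may be understated, by an amount that cannot be derived from them. The ICER would then be too low provided the dressing arm has the better effect, which is the planning assumption.

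The only size that rests on the plan's own figures is EUR 20 per ulcer averted for each EUR 1 of uncounted labour. The span from zero to about EUR 5,400 rests on assumed times, frequencies, durations and wages. With no total cost or decision threshold in the plan, none of these shifts can be shown to change a conclusion. The primary outcome, its test and the sample size are untouched.

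**What to change.** In sections 3.4 and 5.2:

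- Keep application-only labour as the base case.
- Report the ICER a second time with ward-nurse dressing-check time added to the dressing arm. Cost it as approximate turns (from the recorded mean length of position) × an estimated unit time × wage, with the unit time varied over a stated range that includes zero.
- Leave the once-daily researcher visits out, and say that this is because they are trial-driven.
- Carry the same line into the heel and sacral repeats of the analysis.

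The cost is one more estimated input and one line in the cost table. Application time is already an estimate, so the method is not new, and there is no added patient burden and no change to care. The downsides are that the turn count is approximate and that the second ICER may look less favourable to the dressing.

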## Appendix 4: NPUAP/EPUAP pressure ulcer classification 2014

[figure not shown]
# INTERNATIONAL NPUAP/EPUAP PRESSURE ULCER CLASSIFICATION SYSTEM

A pressure ulcer is localized injury to the skin and/or underlying tissue usually over a bony prominence, as a result of pressure, or pressure in combination with shear. A number of contributing or confounding factors are also associated with pressure ulcers; the significance of these factors is yet to be elucidated.

### Category/Stage I: Nonblanchable Erythema

Intact skin with non-blanchable redness of a localized area usually over a bony prominence. Darkly pigmented skin may not have visible blanching; its color may differ from the surrounding area.

The area may be painful, firm, soft, warmer or cooler as compared to adjacent tissue. Category/Stage I may be difficult to detect in individuals with dark skin tones. May indicate "at risk" individuals (a heralding sign of risk).

[figure not shown]

### Category/Stage II: Partial Thickness Skin Loss

Partial thickness loss of dermis presenting as a shallow open ulcer with a red pink wound bed, without slough. May also present as an intact or open/ruptured serum-filled blister.

Presents as a shiny or dry shallow ulcer without slough or bruising.\* This Category/Stage should not be used to describe skin tears, tape burns, perineal dermatitis, maceration or excoriation.

[figure not shown]
*\*Bruising indicates suspected deep tissue injury.*

### Category/Stage III: Full Thickness Skin Loss

Full thickness tissue loss. Subcutaneous fat may be visible but bone, tendon or muscle are not exposed. Slough may be present but does not obscure the depth of tissue loss. May include undermining and tunneling.

The depth of a Category/Stage III pressure ulcer varies by anatomical location. The bridge of the nose, ear, occiput and malleolus do not have subcutaneous tissue and Category/Stage III ulcers can be shallow. In contrast, areas of significant adiposity can develop extremely deep Category/Stage III pressure ulcers. Bone/tendon is not visible or directly palpable.

[figure not shown]

**Category/Stage IV: Full Thickness Tissue Loss**

Full thickness tissue loss with exposed bone, tendon or muscle. Slough or eschar may be present on some parts of the wound bed. Often include undermining and tunneling.

[figure not shown]
The depth of a Category/Stage IV pressure ulcer varies by anatomical location. The bridge of the nose, ear, occiput and malleolus do not have subcutaneous tissue and these ulcers can be shallow. Category/Stage IV ulcers can extend into muscle and/or supporting structures (e.g., fascia, tendon or joint capsule) making osteomyelitis possible. Exposed bone/tendon is visible or directly palpable.

**Unstageable: Depth Unknown**

Full thickness tissue loss in which the base of the ulcer is covered by slough (yellow, tan, gray, green or brown) and/or eschar (tan, brown or black) in the wound bed.

Until enough slough and/or eschar is removed to expose the base of the wound, the true depth, and therefore Category/Stage, cannot be determined. Stable (dry, adherent, intact without erythema or fluctuance) eschar on the heels serves as 'the body's natural (biological) cover' and should not be removed.

**Suspected Deep Tissue Injury: Depth Unknown**

Purple or maroon localized area of discolored intact skin or blood-filled blister due to damage of underlying soft tissue from pressure and/or shear. The area may be preceded by tissue that is painful, firm, mushy, boggy, warmer or cooler as compared to adjacent tissue.

Deep tissue injury may be difficult to detect in individuals with dark skin tones. Evolution may include a thin blister over a dark wound bed. The wound may further evolve and become covered by thin eschar. Evolution may be rapid exposing additional layers of tissue even with optimal treatment.
